#### Reporting and Documentation of Serious Adverse Events, Serious Adverse Device Effects, and Device Deficiencies

**Serious Adverse Events and Serious Adverse Device Effects** have to be **reported to the Sponsor as soon as possible**. The incidence has to be documented on the **Adverse Event Report form** over the whole time of the investigation including information on the date of onset, treatment and resolution, as well as assessment of both the seriousness and the relationship to the study device based on the evaluation of the investigator. The outcome of such complications has to be documented and any changes in outcome have to be updated during the course of the study. In case of early termination of the study, further follow-up of the study participant shall proceed according to the hospital's standard procedure.

**Device Deficiencies** that did not lead to an adverse event but **could have led** to a medical occurrence if suitable actions had not been taken, if intervention had not been made or if circumstances had been less fortunate shall be **reported to the Sponsor as soon as possible**, as well.

The **Investigator** is responsible for reporting all SAEs, SADEs and Device Deficiencies that could have led to a SADE to the Ethics Committee.

The contact information is as follows:

- Name of the sponsor: ZIMMER (Shanghai) Medical International Trading Co., Ltd.
- Address of the sponsor: [name]
- Contact of the sponsor: [name]

- Contact information of the sponsor: [name]

## 14. Deviations from and Amendments to the Clinical Investigation Plan

### 14.1 Protocol Deviation

- (1) Subjects who fail to meet any of the inclusion criteria, or meet any of the exclusion criteria are included in the clinical trial.
- (2) The subjects do not sign the ICF as required; the subjects only sign the ICF after participation in the trial.
- (3) Test or examinations for safety indicators, primary efficacy indicators or key secondary efficacy indicators are not conducted as required in the protocol.
- (4) The subjects fail to come for follow-up within the time window specified in the protocol.
- (5) Loss to follow-up.
- (6) Serious adverse events are not reported or reported in time.
- (7) Any serious violation of the GCP principles in the implementation of the protocol, such as improper process of obtaining informed consent, etc.

### 14.2 Protocol Amendments

Neither the investigator nor the sponsor shall carry out any behavior that deviates from or changes the protocol without the mutual consent of both the investigator and the sponsor. And the revised clinical trial protocol shall be reviewed by the ethics committee with comments provided based on the revised content. Amendments to the protocol will be submitted to the corresponding ethics committees and regulatory authorities in accordance with relevant regulatory requirements.

## 15. Direct Access to Source Documents

The source documents of this trial include the medical records of subjects, ICFs, subject screening and enrollment log, subject identification code form, medical documents of subjects (such as physical examination reports and chemical test reports, etc.), and usage record form of the investigational medical devices, etc.

The source data of this trial include: name, date of birth, gender, trial identification code of subjects; protocol number, name and model of the investigational medical device; start date for trial screening or enrollment; date of use of the investigational medical device and model; investigator's signature; SAEs and their handling; laboratory specimen collection date, results and report date; physical examination results and report date; monitor's signature.

The monitors, auditors, ethics committees related to the trial and the regulatory authorities may have direct access to these source documents and source data to verify the procedures or data of the trial while conforming to the provisions on confidentiality, and such access is authorized by subjects through signing the written ICF.

## 16. Finance and Insurance

Refer to the statement in the contract signed between the clinical trial institution and the sponsor.

## 17. Clinical Study Report

After the end of the clinical trial, the investigator of each participating site should issue a signed and dated clinical trial summary respectively, which should be submitted to the leading clinical trial institution after reviewed, dated and stamped by the medical device clinical trial management department of such site;

The principal investigator of the leading clinical trial institution should complete a signed and dated clinical trial report according to the summaries, which should then be submitted to the sponsor after reviewed, dated and stamped by the medical device clinical trial management department of the leading clinical trial institution. The clinical trial report should include:

- (1) General information
- (2) Summary
- (3) Introduction
- (4) Objective of the clinical trial
- (5) Method of the clinical trial
- (6) Content of the clinical trial
- (7) General clinical data
- (8) Investigational medical device and control medical device/control diagnosis and treatment method
- (9) Statistical analysis method and evaluation method used
- (10) Clinical evaluation criteria
- (11) Organizational structure of the clinical trial
- (12) Ethical compliance statement
- (13) Results of the clinical trial
- (14) AEs found in the clinical trial and their handling
- (15) Analysis and discussion of clinical trial results, especially for indications, scope of application, contraindications and precautions
- (16) Conclusion of the clinical trial
- (17) Problems and suggestions for improvement
- (18) List of trial personnel
- (19) Other matters to be addressed
- (20) Opinions of the investigator and clinical trial management department of the clinical trial institution;

## 19. Publication Policy

The results of this clinical trial may be published and disclosed as scientific literature. All data on this clinical trial are considered confidential, and proprietary to the sponsor. The investigators may not publish and use the data from this clinical trial for data disclosure without the written permission of the sponsor.

## **20. Responsibilities of Each Party**

### **20.1 Responsibilities of the sponsor**

- (1) The sponsor should be responsible for sponsoring, applying for, organizing, and monitoring the clinical trial, as well as for its authenticity and reliability.
- (2) The sponsor should be responsible for organizing the preparation and modification of the investigator's brochure, clinical trial protocol, ICF, CRF, relevant standard operating procedures and other relevant documents, and responsible for carrying out training necessary for the conduct of the clinical trial.
- (3) The sponsor should select clinical trial institutions and investigators from the qualified medical device clinical trial institutions based on the characteristics of the investigational medical device, and should provide the clinical trial institutions and investigators with the latest investigator's brochure and other relevant documents for them to decide whether they can undertake this clinical trial before signing the clinical trial agreement with the clinical trial institution.
- (4) During the clinical trial, the sponsor should make modifications to the investigator's brochure and other relevant documents in a timely manner if aware of any important information that affects the clinical trial, and should submit the modifications to the ethics committee for approval through the medical device clinical trial management department of the clinical trial institution.
- (5) The sponsor should reach a written agreement with the clinical trial institutions and the investigators on relevant details of the clinical trial.
- (6) The sponsor should be responsible for the safety of the investigational medical device in the clinical trial.
- (7) The sponsor should notify the medical device clinical trial management department of all clinical trial institutions within 5 days, with reasons explained in writing in case of a decision to suspend or terminate the clinical trial.
- (8) The sponsor should ensure that all investigators for conduct of the clinical trial strictly follow the clinical trial protocol, and should point out the problem and urge for corrections if it is found that the clinical trial institutions and investigators fail to comply with relevant laws and regulations, the SOPs and this clinical trial protocol; if there is serious noncompliance or such condition remains uncorrected, the sponsor should terminate the trial and report to the medical products regulatory authority at the level of province, autonomous region, and municipality where the clinical trial institution is located as well as the National Medical Products Administration.
- (9) The sponsor should bear the treatment cost for the subjects who have suffered from injuries or deaths related to the clinical trial as well as the corresponding economic compensation, except that the damage is caused by the fault of the medical institutions and their medical staff in the diagnosis and treatment operations.
- (10) The sponsor should be responsible for the monitoring and audit of the clinical trial.
- (11) For SAEs and MDDs that may lead to SAEs, the sponsor, after being notified, should report to the medical products regulatory authority where the trial is filed and the competent health authority at the same level within 5 working days, and should at the same time, notify other clinical trial institutions and investigators participating in the clinical trial, who should notify their respective ethics committee in a timely manner through the medical device clinical trial management department of their respective clinical trial institution.
- (12) The sponsor should ensure that the clinical data in the electronic clinical database or remote electronic clinical data system is controlled and authentic, and create complete verification documents.

- (13) The sponsor should ensure that the CRF is rigorously and reasonably designed to allow the coordinating investigators to obtain all data of the clinical trial institution in the respective sub-site.

## 20.2 Responsibilities of the clinical trial institutions and investigators

- (1) Before accepting the clinical trial project, the clinical trial institutions should evaluate their relevant resources to decide whether to accept the clinical trial project based on the characteristics of the investigational medical device.
- (2) The clinical trial institutions should properly keep the clinical trial records and essential documents as agreed with the sponsor.
- (3) Investigators in charge of the clinical trial should have corresponding qualifications.
- (4) Before the start of the clinical trial, the medical device clinical trial management department of the clinical trial institutions should cooperate with the sponsor to submit an application to the ethics committee as well as other relevant documents as required.
- (5) Investigators should ensure that the relevant staff involved in the trial are familiar with the principles, scope of application, product performance, handling methods, installation requirements and technical indicators of the investigational medical device, understand the pre-clinical study data and safety data of the investigational medical device, and master the prevention and emergency treatment methods for the risks that may arise from the clinical trial.
- (6) Investigators should ensure that the investigational medical device is only used for the subjects of this clinical trial, without charging any fees.
- (7) Investigators should strictly follow the clinical trial protocol, and should not deviate from or substantially change the protocol without the approval of the sponsor and the ethics committee, or without the approval of the National Medical Products Administration as required. However, reporting may be made subsequently in writing if the subjects are faced with immediate hazards and other emergencies that require immediate mitigation.
- (8) Investigators should be responsible for recruiting subjects, and performing informed consent with the subjects or their guardians.
- (9) Investigators or other personnel involved in the trial should not force or otherwise improperly induce the subjects to participate in the trial.
- (10) When an unexpected AE of the investigational medical device is discovered in the clinical trial, the investigators should work with the sponsor to modify the relevant content of the ICF, and submit to the ethics committee for review in accordance with relevant working procedures, and should ask the affected subjects or their guardians to confirm and re-sign the modified ICF after obtaining approval.
- (11) Investigators should be responsible for making medical decisions related to the clinical trial, and in the event of AEs related to the clinical trial, the clinical trial institutions and investigators should ensure that the subjects are provided with adequate and timely treatment and management.
- (12) In the event of SAEs in the clinical trial, investigators should take appropriate measures to treat the subjects immediately, and at the same time, report in writing to the medical device clinical trial management department of their respective clinical trial institution, which should then notify the sponsor in writing. Adverse events are required to be reported on the Adverse Event Report Form. The completed Adverse Event Report Form must be submitted to the Sponsor in a timely manner. The Investigator or Designee will also promptly provide the Sponsor with any additional requested information required for the Sponsor to comply with regulatory requirements. If applicable per their reporting requirements, the Investigator or Designee will also report applicable adverse event(s) to their EC. The Investigator is responsible for reporting all SAEs, SADEs and Device Deficiencies that could have led to a SADE to the Ethics Committee.
- (13) Investigators should record all AEs that occur and MDDs discovered during the clinical trial, and work with the sponsor to analyze the cause of the events to prepare a written analysis report where opinions

on continuation, suspension or termination of the trial should be proposed, to submit to the ethics committee for review through the medical device clinical trial management department of the respective clinical trial institution.

- (14) Investigators should ensure that the clinical trial data is recorded into the CRF accurately, completely, clearly and in a timely manner.
- (15) The clinical trial institutions and investigators should ensure that the data, documents and records formed during the clinical trial are authentic, accurate, clear and secure.
- (16) The clinical trial institutions and investigators should accept the monitoring and audit of the sponsor as well as the supervision of the ethics committee, and provide all necessary records related to the trial.
- (17) The clinical trial institutions and investigators should notify the subjects, and ensure that the subjects are properly treated and followed up, and should report as required and provide detailed written explanations if the clinical trial needs to be suspended or terminated since it is found that the risks exceed the potential benefits, or sufficient results have been obtained for determining the safety and efficacy of the investigational medical device.
- (18) The clinical trial institutions and investigators should report to the medical products regulatory authority at the level of province, autonomous region, or municipality where the sponsor is located or the National Medical Products Administration if it is found that the sponsor has violated relevant regulations or requests to change the trial data or conclusions.
- (19) At the end of the clinical trial, investigators should ensure that all records and reports are completed, and submit the necessary clinical data as required to their respective clinical trial institution.

**Appendix 1 Lysholm Knee Score [1]**

Items and Scoring Scale	Score
1. Limp	
I have no limp when I walk	5
I have a slight or periodical limp when I walk	3
I have a severe and constant limp when I walk	0
2. Using cane or crutches	
I do not use a cane or crutches	5
I use a cane or crutches with some weight-bearing	2
Putting weight on my hurt leg is impossible	0
3. Locking sensation in the knee	
I have no locking and no catching sensation in my knee	15
I have catching sensation but no locking sensation in my knee	10
My knee locks occasionally	6
My knee locks frequently	2
My knee feels locked at this moment	0
4. Giving way sensation from the knee	
My knee gives way	25
My knee rarely gives way, only during athletics or vigorous activity	20
My knee frequently gives way during athletics or other vigorous activity. In turn, I am unable to participate in these activities.	15
My knee frequently gives way during daily activities.	10
My knee often gives way during daily activities.	5
My knee gives way every step I take.	0
5. Pain	
I have on pain in my knee	25
I have intermittent or slight pain in my knee during vigorous	20
I have marked pain in my knee during vigorous activities	15
I have marked pain in my knee during or after walking more than 1 mile	10
I have marked pain in my knee during or after walking less than 1 mile	5
I have constant pain in my pain	0
6. Swelling	
I have swelling in my knee	10
I have swelling in my knee only after vigorous activities	6
I have swelling in my knee only after ordinary activities	2
I have swelling constantly in my knee	0
7. Climbing stairs	
I have no problems climbing stairs	10
I have slight problems climbing stairs	6
I can climb stairs only one at a time	2
Climbing stairs is impossible for me	0
8. Squatting	
I have no problems squatting	5
I have slight problems squatting	4
I cannot squat beyond a 90 degree bend my knee	1
Squatting is impossible because of my knee	0

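### Appendix 1 awards full Lysholm points for giving way and for swelling to answers worded as having the symptom; lesser point: the device success formula in Appendix 2 does not match its definition

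*Combined protocol and SAP*

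**What the plan says.** The primary endpoint is the Lysholm Knee Score at 6 months (section 5.2.1), evaluated as change from baseline (section 6.1.6.1). Appendix 1 alone gives the items and points, and it cites a source publication for the instrument.

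- **Item 4, giving way.** The 25-point line is "My knee gives way". Below it, at 20 points, is "My knee rarely gives way, only during athletics or vigorous activity". The 10- and 5-point lines are "My knee frequently gives way during daily activities" and "My knee often gives way during daily activities".
- **Item 6, swelling.** The 10-point line is "I have swelling in my knee". Below it, at 6 points, is "I have swelling in my knee only after vigorous activities".
- **Item 5, pain.** The 25-point line is "I have on pain in my knee". The 20-point line breaks off after the word 'vigorous', and the 0-point line names pain, not the knee, as the place of the pain.
- **For contrast, item 3.** The 15-point line is "I have no locking and no catching sensation in my knee".

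Section 6.1.3, item (6), provides for fixed assessors trained in efficacy assessment. The answers are in the first person, and the plan does not say whether the subject or an assessor completes the form.

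Appendix 2 covers immediate device success, a secondary endpoint. In words, success means that the injured site was sutured with no instruments beyond the matching tools. The formula beneath divides anchors implanted with success by all anchors implanted.

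**The concern.** In items 4 and 6 every printed answer states that the symptom is present. A knee that never gives way or never swells therefore has no true option. Conversely, a knee that does give way or swell makes the top line literally true, so the maximum can be ticked honestly. The first problem can lower a good score and the second can raise a poor one. Either could enter the baseline or the 6-month value from which the primary variable is formed.

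This is the scoring rule for the primary endpoint, and a case report form, translation or training session built from Appendix 1 would inherit it.

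In Appendix 2 the words and the formula use different units, and only the words mention extra instruments. The same operation can count as a failure under one and a full success under the other.

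**Working it through.** **Lysholm maximum.** The top points in Appendix 1, items 1 to 8, are 5 + 5 + 15 + 25 + 25 + 10 + 10 + 5 = 100, so the points column is complete and the problem lies in the wording.

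**Which items are affected.** Items 1, 2, 3, 7 and 8 describe the symptom-free state at the top. Item 5 does so too once 'on' is read as 'no'. Only items 4 and 6 do not.

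**Symptom-free knee.** The other six items give 100 − 25 − 10 = 65. If the person scoring takes either the top or the next line in items 4 and 6:

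| Item 4 | Item 6 | Total |
|---|---|---|
| 25 | 10 | 65 + 25 + 10 = 100 |
| 25 | 6 | 65 + 25 + 6 = 96 |
| 20 | 10 | 65 + 20 + 10 = 95 |
| 20 | 6 | 65 + 20 + 6 = 91 |

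The largest difference is 5 + 4 = 9 points for one subject at one scoring. It is an illustration, not a bound: an item left blank or a lower line would give less.

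**Symptomatic knee.** If the top line is ticked because it is literally true, the excess over the line that fits best is 25 minus 20, 15, 10, 5 or 0 in item 4 (5 to 25 points), and 10 minus 6, 2 or 0 in item 6 (4 to 10 points). The documents give no indication of how often this would happen.

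**Appendix 2.** Suppose k anchors are implanted, one further anchor is tried but never implanted, and the repair is finished with another instrument. The definition records a failure. The formula, read literally, gives k/k = 100%, because the failed anchor is not in the denominator. Now suppose the failed anchor is replaced with the same device and the site is sutured without other instruments. The definition records a success. A per-anchor rate over anchors attempted, with k + 1 implanted out of k + 2 attempted, is below 100%. A site-based rate can therefore lie below or above an anchor-based one.

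Sections 6.1.4 and 8.2.2.4, items (6) and (8), have anchor use, device quantity, a performance evaluation and deficiencies recorded. They do not name anchors attempted or extra instruments used.

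**The case against.** The strongest reply is that this is an editorial slip that the table itself resolves. Points fall from line to line, so the line above "My knee rarely gives way, only during athletics or vigorous activity" can only mean a knee that does not give way, and the same holds for item 6. The other six items follow that pattern and the instrument is cited. Someone who sees the order awards 25 and 10, total 100. For a symptom-free knee the 20- and 6-point lines are as untrue as the top lines, so a literal reading gives no special reason to choose 91. All of this stands, and it is why the 9 points are only an illustration.

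It is also fair that the case report form is a separate sponsor document (section 20.1, items (2) and (13)), that assessors are trained, and that nothing says Appendix 1 is the training text. The cut-off 20-point line in item 5 may come from text extraction. That is less likely for the top lines of items 4 and 6, which are whole sentences with their points in place. Whether the near-identical 10- and 5-point lines of item 4 are errors depends on the cited instrument, which is not in the documents.

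Three stronger readings are tempting and not supported:

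- **That 9 points exceeds the non-inferiority margin** (5.1 in section 7.2.1, 8 in section 7.5). This sets one subject's spread against a difference between group means. A misreading shared by both arms would largely cancel in that difference.
- **That the trial is biased or loses power.** Any such figure needs an assumed share of misread forms, and the documents give none.
- **That 94 × 4 = 376 scorings, or the 94 × 2 = 188 behind the primary endpoint, are affected.** The number may be zero. The baseline scorings are of knees scheduled for repair, which are unlikely to be symptom-free.

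On Appendix 2, the word for success in the numerator suggests that the denominator was meant to include failed attempts. That would settle the denominator, but not the unit or the missing condition on extra instruments.

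**Conclusion.** The point holds as a defect in the text of the primary endpoint's scoring rule. Two of the eight items have top answers that say the opposite of what is almost certainly meant, and item 5 has misprints. The illustrated size is up to 9 points in one subject's total (91 instead of 100), assuming a symptom-free knee and the next line taken in both items. The reverse error, over-scoring a symptomatic knee, is also possible under a literal reading; its frequency is unknown. No direction of bias, no loss of power and no count of affected scorings can be stated, because the site form is not in the documents and the intended meaning can be guessed. The sample size is not touched.

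The Appendix 2 mismatch is real but lesser. The definition and the formula measure different things. No difference in rates can be estimated, because the documents give no count of failed anchors or extra instruments. It should still be fixed because the correction is nearly free.

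**What to change.** **Appendix 1.**
- Reword the top answers of items 4 and 6 as the symptom-free state, and correct 'on' to 'no' in the top answer of item 5.
- Check every line of Appendix 1 against the cited instrument, including the 20- and 0-point lines of item 5 and the 10- and 5-point lines of item 4.
- Check the case report form or site form in the same way.
- Only if the site form carries the wording, list the scorings made on it.

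**Appendix 2.**
- Report the proportion of sites or subjects sutured with the assigned device and without extra instruments, other than the matching tools, over those in which that device was attempted. The sponsor should state the unit.
- Give any per-anchor rate over anchors attempted.
- Confirm that the case report form records anchors attempted and extra instruments used.

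**Cost.** A few wording corrections, one formula and one form check, with possibly one extra case report form field. If the subject is the unit, the rate moves in coarser steps of 1/47, about 2.1 percentage points per subject in each arm. The reported rate may go up or down.
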